12.3 Visits in Pre-treatment period

All visits will be scheduled between 9:00am and 5:00pm.

12.3.1 Screening Visit

The following screening procedures will be performed at the screening visit:

• Each participant must sign an IRB-approved informed consent form before any of the study-related procedures can be performed. The original signed informed consent form will be kept on file by the investigator with the subject's record and a signed copy will be given to the subject.

- A screening number will be assigned.
- A general medical history will be taken and will include information on current and previous diseases and treatment.
- Vital signs (pulse, blood pressure and respiratory rate) will be taken and recorded.
- Complete physical exam including measurement of testicular volume will be performed.
- Fasting blood samples will be obtained for the following measurements: Complete blood count (CBC), clinical chemistry including glucose, liver and renal function tests (urea, creatinine, albumin, alanine aminotransferase, aspartate aminotransferase, gamma glutamine transferase, alkaline phosphatase, bilirubin, albumin, full lipid panel including total cholesterol, HDL, and LDL, triglycerides, hematology (hematocrit, hemoglobin), and hormones (LH, FSH, T)
- Semen analysis will be done to measure sperm concentration, motility and morphology
- Height and weight will be collected
- Participants will be questioned regarding concomitant medications and adverse events.
- Once lab results are obtained and considered consistent with idiopathic infertility by the investigator as per the inclusion/exclusion criteria for enrollment, the participant is informed by telephone of his lab results. If conformance to the inclusion/exclusion is confirmed, he is scheduled to return to the clinic for the 2nd sperm collection. If this 2nd sperm collection also meets enrollment criteria, the subject is schedule to begin on treatment
- Successful volunteers will be assigned subject numbers in sequence as they meet the study requirements.
- If any results are abnormal, according to local laboratory standards and in the clinical judgment of the investigator, the subject will be informed and excluded from the study and referred to his primary physician.

12.4 Visits in treatment period

Seven visits will occur in the treatment period: week 0, week 4, week 8, week 12, week 16, week 20 and week 24. All visits are \pm 4 days.

12.4.1 Visit 1 (week 0)

This is the day 1 of treatment. The following will be done at this visit:

- Vital signs (pulse, blood pressure, respiratory rate) and weight will be taken and recorded.
- Subjects will be questioned regarding concomitant medications and adverse events. If the subject is taking a medication that is listed as disallowed the subject should not be enrolled in the study.
- The subject will complete the PHQ9 questionnaire (see appendix xx)
- A blood samples will be drawn, and the time of day of the blood draw will be noted in the CRF.
- A semen sample will be obtained for the measurement of sperm count, concentration, motility and morphology.
- Subjects will be given enough supply of study medication for 30 days (plus a supply for 2 additional days in the event of scheduling issues) as per their assigned group.
- A study medication log will be dispensed to record the date and time of administration of the study medication. Subjects will be instructed to take the medication in the morning, except on the day of the visit. Subjects will be scheduled to return to the clinic after 28 ± 4 days.

12.4.2 Visits 2-7

These visits are for weeks 4,8,16, 20 and 24. The following procedures will be done at each of these visits:

- Vital signs (pulse, blood pressure, respiratory rate) and weight will be taken and recorded.
- The subject will complete the PHQ9 questionnaire
- Complete physical exam including testicular examination and volume measurement will be performed.
- Subjects will be questioned regarding concomitant medications and adverse events.
- Any unused study medication will be collected at this visit.
- Study medication log will be reviewed to check the date and time of drug administration. These logs will be collected at this visit.

 A blood sample will be drawn. The time of day of the blood draws will be recorded in the source.

- A semen sample will be obtained for the measurement of sperm count, concentration, motility and morphology
- Fasting blood samples will be obtained for the following measurements: CBC, clinical chemistry including glucose, liver and renal function tests (urea, creatinine, albumin, alanine aminotransferase, aspartate aminotransferase, gamma glutamine transferase, alkaline phosphatase, bilirubin, and albumin), full lipid panel including total cholesterol, HDL and LDL, triglycerides, hematology (hematocrit, hemoglobin), and testosterone, FSH and LH. In addition, two serum samples will be frozen for the future analysis of serum retinoid levels.
- Subjects will be given the next month's supply of medication.
- Subjects will be scheduled to return to the clinic after additional 4 weeks visit.

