We will conduct a prospective, three-arm, randomized, double-blinded, placebo-controlled interventional trial to determine the impact of therapy with 13-cis retinoic acid on sperm indices in infertile men. Sixty (n=20/group) infertile men with abnormal sperm analyses will be enrolled in a 24-week study of 20mg or 40 mg of 13-cis retinoic acid or matching placebo daily. The subjects will be closely followed for side effects related to treatment. The impact of treatment on indices of spermatogenesis will be determined by monthly seminal fluid analyses. All aspects of this study will be performed in compliance with Good Clinical Practice (GCP) regulations, ICH guidelines, the Declaration of Helsinki, and under an FDA Investigational New Drug (IND) application.

6. Duration of the Study

Subjects: Subjects will undergo a screening phase of up to 60 days. After fulfilling all entry criteria, the first 60 subjects will be randomly assigned to one of the three groups. The treatment phase will last for 24 weeks and subjects will have two post-treatment visits, about 4 and 12 weeks after the end of treatment.

Enrolment should be completed in approximately 12 months, resulting in total study duration of about 24 months including screening, treatment phase, end of study visit procedures, close out and data analysis.

7. Number of Subjects

60 men will participate in the study (n=20/arm)

8. Dosage and Administration

13-cis retinoic acid at 20 or 40 mg daily (purchased commercially) or matching placebo

9. Selection of Subjects

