11.1 Study Medication

Each subject will receive the study medication assigned per the randomization list. The first dose will be administered at the clinic under the observation of the study staff. The day and time of the start of treatment will be recorded on the CRF in the appropriate space provided. The subjects will be given enough supply of medication (for 28 days) until their next visit.

Study medication log (diary) will be provided to the subjects for recording the time of application of gel. These medication logs will be reviewed at each visit. The investigator will retain the copies of these logs.

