12.1 General

There will be a total of three treatment groups as described in Section 7. The study will consist of 3 periods:

- 1. Pre-treatment period (including screening) for up to 60 days.
- 2. Treatment period for 24 weeks

3. Recovery period for about 12 weeks

The treatment period will begin with Day 1 of treatment, daily for 24 weeks. The recovery period will last for about 12 weeks.

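### Section 12.4.2 gives out a further month of study drug at every visit from 2 to 7, week 24 included, which contradicts the 24-week treatment period

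*Combined protocol and SAP*

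**What the plan says.** Two groups of statements in the combined protocol and SAP bear on this.

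**Length of treatment.** Section 12.1: "The treatment period will begin with Day 1 of treatment, daily for 24 weeks". Section 6 gives the same length and adds that "subjects will have two post-treatment visits, about 4 and 12 weeks after the end of treatment". The synopsis also gives a 24-week active phase. Appendix 1 places the two follow-up visits at weeks 28 and 36.

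**Dispensing.**
- Section 11.1: "The subjects will be given enough supply of medication (for 28 days) until their next visit".
- Section 12.4.1, for week 0: "enough supply of study medication for 30 days (plus a supply for 2 additional days" to allow for scheduling problems.
- Section 12.4.2, headed for visits 2 to 7: "These visits are for weeks 4,8,16, 20 and 24". It continues: "The following procedures will be done at each of these visits". One item on that list is "Subjects will be given the next month's supply of medication". The next item brings the man back after a further 4 weeks.
- Appendix 1, as extracted from the PDF, marks dispensing only at the week-0 visit. It marks collection of unused drug and of the medication log only at visits 2 to 7.
- Section 12.4.3, for the follow-up visits, lists no collection of drug or logs.

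Section 12.4 gives the full visit list: "Seven visits will occur in the treatment period: week 0, week 4, week 8, week 12, week 16, week 20 and week 24". The weeks named in section 12.4.2 leave out week 12.

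**The concern.** A site coordinator working through section 12.4.2 at the week-24 visit is told to hand over another month of drug and book a return in 4 weeks. Nothing in that section marks week 24 as the last treatment visit. A coordinator working from sections 6 and 12.1 would treat it as the end of dosing. Both cannot be followed as written.

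Four things are at stake:
- exposure to study drug beyond the stated period;
- the meaning of the week-28 and week-36 samples (semen, reproductive hormones and retinoids, section 12.4.3), which are described as post-treatment;
- drug accountability: section 11.3 requires unused drug to be returned, but no collection is listed after week 24, and no log would be collected for doses taken after that visit;
- the secondary endpoint in section 14 that counts pregnancies occurring on treatment, whose window would close at week 24 or at week 28 depending on the section followed.

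**Working it through.** **Inputs.** Treatment length 24 weeks = 24 × 7 = 168 days (sections 6 and 12.1). Supply per dispensing 28 days (section 11.1). Treatment visits at weeks 0, 4, 8, 12, 16, 20 and 24 (section 12.4). Follow-up at weeks 28 and 36 (Appendix 1), that is days 28 × 7 = 196 and 36 × 7 = 252.

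**Step 1: reproduce the stated duration.** Days covered = number of dispensings × 28. Dispensing at weeks 0, 4, 8, 12, 16 and 20 gives 6 × 28 = 168 days = 24 weeks. Follow-up then falls 28 − 24 = 4 and 36 − 24 = 12 weeks after the end of treatment, as section 6 says. These figures agree only when nothing is dispensed at week 24.

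**Step 2: add the week-24 dispensing in section 12.4.2.** 7 × 28 = 196 days = 28 weeks. Extra exposure is 28/168 = 16.7%, about 17%.

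**Step 3: time off drug at follow-up, if the week-24 supply is taken in full.**

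| Visit | Stated | With week-24 supply taken |
|---|---|---|
| Week 28 (day 196) | about 4 weeks | 196 − 196 = 0 days |
| Week 36 (day 252) | about 12 weeks | 252 − 196 = 56 days = 8 weeks |

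**Step 4: sensitivity to supply size.** Section 12.4.2 says only a month. The 30 and 32 days come from week 0 (section 12.4.1), and applying them at week 24 is an assumption. The supply would then end on day 168 + 30 = 198 or 168 + 32 = 200, which is 2 or 4 days after the week-28 visit. If the ±4-day window, stated only for treatment visits, also applied at week 28, a 28-day supply would run out between 4 days before and 4 days after the sample.

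**Step 5: the other dispensing statements, taken literally.**
- The weeks named in section 12.4.2, plus week 0, are 0, 4, 8, 16, 20 and 24. That is again 6 × 28 = 168 days of drug, but with no supply from week 12 to week 16 and with the last supply ending on day 196. The 17% in step 2 therefore assumes that week 12 is also a dispensing visit, as the section's heading and section 12.4 imply.
- Appendix 1 as extracted has one dispensing, at week 0. Even at 32 days this covers 32/7 = 4.6 weeks of a 24-week treatment.

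No two of section 12.4.2, Appendix 1 and the 24-week total describe the same dispensing schedule.

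**The case against.** The best reply is that this is a drafting slip in a shared list. The 24-week duration is stated consistently in the synopsis, sections 6 and 12.1 and the primary endpoint. Appendix 1 labels weeks 28 and 36 as follow-up. A supply for the next month presupposes a next month of treatment, and at week 24 there is none. The section is loose in other ways too, since it drops week 12. Most readers would take the intended meaning from the surrounding text.

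Much of this stands. Nothing else in the documents plans dosing after week 24, so the extra exposure follows from the wording and is not a stated plan. It also takes two further steps: a site must apply the list literally, and men must keep dosing past the stated 24 weeks.

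A reader might go further and infer that recovery could no longer be assessed, or that the trial's main result is at risk. The documents support neither. Week 36 would still be about 8 weeks off drug. Recovery and reversibility are not among the objectives in section 2 or the endpoints in section 14, and no efficacy analysis of weeks 28 or 36 is specified. The primary endpoint is taken at week 24, before any week-24 supply could be used.

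The reply does not remove the conflict. The item is an operative instruction, it has no exception, the return visit listed after it fits week 28, and section 11.1 ties supply to the next visit and not to the end of treatment. Appendix 1 does not settle the matter, because it conflicts with section 12.4.2 at weeks 4 to 20 as well.

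**Conclusion.** The contradiction is in the current text and can be stated with high confidence: section 12.4.2 dispenses at week 24, while sections 6 and 12.1 end treatment there.

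If followed literally, its size is up to about 4 weeks of added exposure (168 to 196 days, about 17%), with the two follow-up samples about 0 and 8 weeks off drug instead of 4 and 12. This rests on 28-day supplies, dispensing at every treatment visit including week 12, and the week-24 supply being taken in full. How likely that is cannot be judged from the documents.

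The consequences are limited to the post-treatment samples, drug accountability and the pregnancy-counting window. The point should be corrected, but it does not bear on the validity of the primary analysis. The Appendix 1 dispensing row needs care, because the table was read from a PDF.

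**What to change.** Reconcile sections 6, 11.1, 12.1, 12.4.1, 12.4.2 and Appendix 1 so that together they state one dispensing schedule. It should say:
- at which visits drug is dispensed, and explicitly whether week 24 is one of them;
- the size of each supply, settling 28 days against 30 plus 2;
- whether week 12 belongs to the visits covered by section 12.4.2.

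Add a matching schedule for collecting unused drug and medication logs in sections 12.4.2 and 12.4.3 and Appendix 1, so that any drug issued has a planned return visit. State the end of treatment once, so that the pregnancy window in section 14 can refer to it.

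Which dispensing rule applies is for the sponsor and investigator to decide. The cost is protocol wording; no added analysis is needed.

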12.4.3 Visit 8 and 9 (Follow-up Visits)

The following will be done at this visit:

- Vital signs (pulse, blood pressure and respiratory rate) will be taken and recorded.
- The subject will complete the behaviour questionnaire
- Subjects will be questioned regarding concomitant medications and adverse events.
- A blood sample will be drawn for the measurement of serum FSH, LH, T, and retinoids.
- A semen sample will be obtained for the measurement of sperm count, concentration, motility and morphology

13. Study Withdrawals

Subjects withdrawing from the study can be replaced only if the withdrawal occurs before the start of the treatment. Subjects who have had medication will not be replaced, regardless of the reason for discontinuation. All efforts should be made to contact any subject who decides to discontinue study participation for the end of study safety procedures (Visit 9). The necessary clinical and laboratory examinations planned at the last visit should be performed at the end of the study whenever it occurs. The reasons for discontinuation will be documented.

Post-Admission Withdrawal Criteria

Subjects may be discontinued prematurely for any of the following reasons:

• Emergence of a severe condition(s) such that, in the judgment of the investigator, continuation in the trial would negatively impact the health of the subject.

- Personal reasons (e.g. withdrawn consent).
- Subject lost to follow-up

All subjects in a treatment arm may be discontinued prematurely if greater than 25% of the subjects in an arm are discontinued for the emergence of the same severe condition that requires individual subjects to be discontinued.

14. Statistical Considerations

Data analysis and Interpretation of Results: The primary endpoint is the count of total motile spermatozoa in the ejaculate at week 24 of treatment compared with baseline. Secondary endpoints include other changes in sperm quality, and any pregnancies occurring during treatment as well as the incidence of side effects. The number of total motile sperm after six months of treatment will be compared between the three groups using a Kruskal-Wallis ANOVA with a Wilcoxon rank-sum post-hoc test. The change in the total motile sperm count from baseline (a secondary endpoint) will be performed with a Wilcoxon sign-rank test. Linear regression will be performed to determine if significant relationships between baseline (or delta) retinoic concentrations and changes in sperm quality are present using STATA Version 10.0 (College Park, TX, USA). For all comparisons, an alpha of 0.05 will be considered significant.

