Criteria	Klinefelter syndrome or Y-chromosome microdeletions), hypogonadotropic hypogonadism (that might respond to gonadotropin injections), the use of anabolic steroids, illicit drugs, or the consumption of more than 4 alcoholic beverages daily, severe mental health problems, or current therapy with retinoic acid (e.g. Accutane) or vitamin A.

Efficacy	In this study, count of total, motile sperm after 24 weeks of
Parameters	treatment.
Safety	CBC, clinical chemistry panel (glucose, liver and renal
Parameters	function tests including urea, creatinine, albumin, alanine aminotransferase, aspartate aminotransferase, alkaline phosphatase, bilirubin), full lipid panel including Total cholesterol, HDL, LDL, triglycerides at screening and at the end of treatment. Additional measures will be conducted if any abnormal values are found until the end of study visit. • Adverse event and concomitant medications throughout the study. Other safety parameters include vital signs; and changes in pre- and post-treatment physical examination results and score on the PHQ9 depression questionnaire.
Evaluations	The following determinations will be made in all subjects: • Serum samples will be collected for the measurement of concentrations of vitamin A, all-trans and 13-cis retinoic acid, testosterone, FSH and LH will be collected before the beginning of the treatment, and monthly during treatment.
Other Assessments	Demographic characteristics, including age and race, will be collected
Statistical	The primary endpoint is the effect of treatment on the count
	of total, motile sperm between treatment groups after 24
Analysis	weeks. This analysis will be conducted using a Kruskal-Wallis ANOVA is the primary endpoint.

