14.1 Sample size consideration

Inclusion of 20 men per group will allow for an 80% power to detect a greater than a 20% difference for total motile sperm count at week 24 compared with placebo with a variance of 25% and allowing for a drop-out rate of 10% at an alpha of 0.05.

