14.2 Efficacy

Primary: The primary efficacy outcome is increase in the count of total, motile sperm after twenty-four weeks of study treatment.

Secondary: The magnitude and changes between baseline and week 24 in terms of total, motile sperm count will be described for subjects in each treatment arm.

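### The valid between-arm test of the week-24 count uses none of three pre-treatment counts; the endpoint sentence is loosely worded, and baseline is undefined for the secondary within-arm test

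*Combined protocol and SAP*

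**What the plan says.** Section 14 (Statistical Considerations) opens its endpoint definition with "The primary endpoint is the count of total motile spermatozoa in the ejaculate at week 24 of treatment compared with baseline". It then states the analysis: "The number of total motile sperm after six months of treatment will be compared between the three groups using a Kruskal-Wallis ANOVA", followed by Wilcoxon rank-sum post-hoc tests. Next it gives a different status to change from baseline: "The change in the total motile sperm count from baseline (a secondary endpoint) will be performed with a Wilcoxon sign-rank test". It closes with "For all comparisons, an alpha of 0.05 will be considered significant".

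The synopsis puts the primary comparison on the count "of total, motile sperm between treatment groups after 24" weeks and names Kruskal-Wallis as the analysis. Section 14.1 sizes the trial to "detect a greater than a 20% difference for total motile sperm count at week 24 compared with placebo with a variance of 25"%. Section 14.2 gives the primary as "The primary efficacy outcome is increase in the count of total, motile sperm after twenty-four weeks of study treatment" and lists change as secondary: "The magnitude and changes between baseline and week 24 in terms of total, motile sperm count will be described".

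Three semen samples precede treatment. Two are screening samples (sections 9.1.1 and 12.3.1, Appendix 1), and both must show a total motile count below 10 million. The third is taken at Visit 1, Day 1 of treatment (section 12.4.1), and is not an eligibility sample. No section says which sample, or which average, is the baseline.

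**The concern.** There are three linked points, of unequal weight.

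- **Precision.** The primary test compares week-24 counts alone. Counts from the same man are likely to be correlated over time, so pre-treatment counts can remove between-man variation from the comparison. With so few men, that information is worth having.
- **Definition of baseline.** The signed-rank test cannot be run until a baseline is chosen. The screening counts were selected to be low. If they are used, later counts can drift up through regression to the mean, and an arm may appear to improve with no drug effect.
- **Wording.** The opening sentence of section 14 mentions baseline, while the test that follows does not involve it and change from baseline is labelled secondary.

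**Working it through.** **The plan's own figure.** Section 14.1 claims 80% power with 20 men per arm, a 20% difference, 10% drop-out and alpha 0.05. I read its 25% variance as an SD of 25% and take alpha as two-sided; the section states neither. By the normal approximation, 25 evaluable men per arm are needed (28 enrolled), and 18 evaluable men (20 × 0.9) give 67.0% power; the t-test gives 64.5%. A one-sided test with all 20 men evaluable gives 81.2%, which leaves nothing for drop-out. So the stated figure is not reproduced. That is a separate matter, and nothing below depends on it.

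**Gain from adjustment, pairwise against placebo.** Inputs are n = 18 per arm, difference 0.20 and SD 0.25. The correlation rho between the pre-treatment and week-24 counts is not in the documents, so I assume 0.3 to 0.7. The adjusted SD is 0.25 × √(1 − rho²). The noncentrality is 0.20 / (adjusted SD × √(2/18)). Degrees of freedom are 34 unadjusted and 33 with one covariate.

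| rho | √(1 − rho²) | noncentrality | power |
|---|---|---|---|
| unadjusted | 1 | 2.400 | 64.5% |
| 0.3 | 0.954 | 2.516 | 68.5% |
| 0.5 | 0.866 | 2.771 | 76.7% |
| 0.7 | 0.714 | 3.361 | 90.3% |

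**Gain on the three-group rank test, by simulation.** All inputs are assumed: 6,000 replicates, 18 men per arm, log-normal counts with equal correlation between samples, both screening counts below 10 million, counts below 0.5 million set to zero, and both doses raised by 20%. The source median is the median before selection. Results at log SD 0.25:

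| Source median (million) | rho | Kruskal-Wallis | Rank ANCOVA, Day 1 | Rank ANCOVA, mean of three |
|---|---|---|---|---|
| 2 | 0.3 | 55.1% | 58.8% | 62.5% |
| 2 | 0.5 | 55.2% | 66.8% | 74.8% |
| 2 | 0.7 | 55.6% | 81.9% | 90.8% |
| 5 | 0.3 | 56.0% | 59.2% | 63.4% |
| 5 | 0.5 | 56.2% | 68.0% | 75.2% |
| 5 | 0.7 | 56.1% | 82.9% | 91.4% |
| 10 | 0.3 | 60.4% | 62.7% | 64.1% |
| 10 | 0.5 | 67.2% | 73.0% | 76.0% |
| 10 | 0.7 | 78.2% | 87.8% | 91.8% |

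With the three-sample mean, the gain at a median of 10 million is 64.1 − 60.4 = 3.7, 76.0 − 67.2 = 8.8 and 91.8 − 78.2 = 13.6 points. At medians of 2-5 million it is about 7, 19-20 and 35 points. At log SD 1 with the same 20% difference, Kruskal-Wallis has about 7-9% power and the adjusted tests about 8-13%. Type I error across 18 scenarios was 4.0-5.2% for Kruskal-Wallis, 4.4-5.4% with Day 1 and 4.6-5.6% with the three-sample mean.

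**False increase in the signed-rank test.** This assumes no drug effect, arms of 18 men and a nominal 2.5% in the upward direction.

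- Against the mean of the two screening counts: 2.1-2.7% at a median of 2 million and log SD 1; 1.8-2.5% at medians of 2-5 million and log SD 0.25; about 5-17% at 5 million and log SD 1. It is higher still when the source median lies at the cut-off.
- Against Day 1: about 2-3% throughout.

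**The case against.** The strongest reply is that the plan already settles the primary. The synopsis names Kruskal-Wallis between groups, section 14.1 is powered against placebo, and sections 14 and 14.2 both call change from baseline secondary. No section attaches a before-after test to the primary. This stands. A reader might infer from the first sentence of section 14 that the primary is a within-arm comparison, but the rest of the plan does not support that. The word increase in section 14.2 can mean an increase relative to placebo. Nor do sections 14 and 14.2 conflict because one tests the change and the other describes it: a secondary endpoint can be both.

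It is also fair to say that omitting the pre-treatment counts is a loss of efficiency, not an error, and that its size rests on a correlation the documents do not give. The largest gains need both the plan's small spread and rho near 0.7. The three-sample mean also looks best when screening samples a week apart correlate no better with each other than with week 24. In a run at median 5 million, log SD 0.25 and rho 0.5, raising the correlation among pre-treatment samples to 0.7-0.8 cut its power from 73.5% to 70-71%, against 67-68% for Day 1. At rho 0.3 it fell from 63% to 60-61%. These limits bear on the size of the gain. They do not remove the case for using data already in hand.

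Regression to the mean arises only if screening counts are taken as baseline although a Day 1 sample exists, and only with a spread well above 25% at medians of 2-5 million. This too stands.

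**Conclusion.** The point holds as one of efficiency and definition. The primary test is valid and leaves usable information aside. At the plan's own SD and difference, with 18 men per arm, pairwise power would rise from 64.5% to between 68.5% and 90.3%. The three-group rank test would rise from about 55-56% to 59-83% with Day 1 as covariate, or 62-91% with the three-sample mean, at source medians of 2-5 million. The gain is smaller at 10 million and slight at log SD 1. All of this rests on an assumed correlation of 0.3-0.7 and on assumed distributions.

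Two stronger inferences are not supported. The eligibility cut-off does not bias the randomized comparison, because it applies equally to all arms; the undefined baseline affects only the secondary within-arm test. And adjustment cannot be relied on to restore 80% power: the pairwise figures at rho 0.3 and 0.5 stay below it.

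**What to change.** 1. **Wording.** In section 14, state: *The primary endpoint is the total motile sperm count in the ejaculate at week 24, compared between the three arms.* Align section 14.2 with it.
2. **Baseline for change.** Define it as the Day 1 sample, collected before the first dose. Sections 11.1 and 12.4.1 do not state that order, so it must be written in. Keep the signed-rank test as secondary, and say that a within-arm change is not evidence of a treatment effect.
3. **Primary analysis.** Pre-specify rank ANCOVA. Rank the week-24 counts over all three arms, with average ranks for ties. The covariate is the rank of the mean of each man's available pre-treatment counts, under its own name so that it is not confused with the Day 1 baseline for change. The two-degree-of-freedom arm test at two-sided 0.05 is primary. It is followed by covariate-adjusted comparisons of each dose with placebo from the same model, in place of the unadjusted rank-sum post-hoc tests, because section 14.1 powers the comparison with placebo. Report Kruskal-Wallis with rank-sum tests as a sensitivity analysis.

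The cost is a few sentences, one degree of freedom and a slightly less simple test. No visits, samples or men are added. Eligibility already requires two screening counts, so a missing Day 1 sample would not remove a man from the primary analysis. Settle it before unblinding.

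### Change in total motile sperm count from baseline is tested only by a paired signed-rank test, so change on drug is never compared with change on placebo (minor)

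*Combined protocol and SAP*

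**What the plan says.** Section 14 (Statistical Considerations) names one test for change: "The change in the total motile sperm count from baseline (a secondary endpoint) will be performed with a Wilcoxon sign-rank test". It does not say whether the test is run by arm or on all men pooled. Section 14.2 points to by arm: "The magnitude and changes between baseline and week 24 in terms of total, motile sperm count will be described for subjects in each treatment arm".

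The between-arm test in section 14 has a different variable: "The number of total motile sperm after six months of treatment will be compared between the three groups using a Kruskal-Wallis ANOVA", followed by a rank-sum post-hoc test. A regression in the same section looks for "significant relationships between baseline (or delta) retinoic concentrations and changes in sperm quality"; its predictor is a concentration, not the randomised arm. Section 14 closes with "For all comparisons, an alpha of 0.05 will be considered significant", without stating one- or two-sided.

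The status of change is not settled. Section 14 opens with "The primary endpoint is the count of total motile spermatozoa in the ejaculate at week 24 of treatment compared with baseline" and 14.2 says "The primary efficacy outcome is increase in the count of total, motile sperm after twenty-four weeks of study treatment", yet section 14 then labels change secondary. The synopsis words the primary analysis for the count "of total, motile sperm between treatment groups after 24" weeks, and the sample size in 14.1 is also set on week 24 against placebo.

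**The concern.** The trial randomises men to placebo so that movement common to all arms can be separated from a drug effect. A within-arm test cannot make that separation. If counts drift in every arm, for whatever reason, the signed-rank p-value in an active arm reflects drift plus drug effect. Separate p-values by arm then invite the reading that drug worked because the active arm was significant and placebo was not. That pattern can arise with no drug effect, and a shared decline can mask a real effect in the within-arm p-value.

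This matters because the plan gives change a formal test at 0.05, and some of its wording makes change sound like the main efficacy question. At stake is the validity of the inference on the change endpoint, not the validity of the trial.

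**Working it through.** **Step 1. Match each analysis to its variable and comparison.**

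| Analysis | Variable | Compared with placebo? |
|---|---|---|
| Kruskal-Wallis, then rank-sum (14) | count after six months | yes |
| Signed-rank (14) | change from baseline | no, paired within men |
| Linear regression (14) | change in sperm quality against retinoic acid concentration | no |
| Description by arm (14.2) | change, baseline to week 24 | no test |

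No row tests change between arms.

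**Step 2. Inputs for an illustration.** From section 7 and 14.1: 20 men per arm and 10% drop-out, so 20 × 0.9 = 18 evaluable; a 20% design difference; alpha 0.05, taken as two-sided. Assumed: the stated variance of 25% is an SD of 25% of the mean; baseline to week-24 correlation ρ of 0.3, 0.5 or 0.7; normally distributed changes. The documents give no drift and no ρ.

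The plan's own figure on these inputs: n = 2 × (1.960 + 0.842)² × (25/20)² = 24.5, so 25 per group, or 28 after drop-out (25/0.9 = 27.8). The stated 20 is not reproduced two-sided. That is a separate matter; 14.1 is used here only for scale.

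**Step 3. SD of change** = 25% × √(2(1 − ρ)) = 29.6%, 25.0% and 19.4% of the mean.

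**Step 4. No drug effect, shared rise of 10%.** Let p be the chance that the exact signed-rank test (18 men) shows a significant rise in one arm. By simulation (20,000 replicates) p = 0.259, 0.344 and 0.516 for the three values of ρ. Arms are independent, so:

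- A given active arm up, placebo not: p(1 − p) = 0.259 × 0.741 = 0.19; 0.344 × 0.656 = 0.23; 0.516 × 0.484 = 0.25.
- Either active arm up, placebo not: [1 − (1 − p)²](1 − p) = 0.33, 0.37, 0.37. Direct simulation gave 0.340, 0.377, 0.371.

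With a shared rise of 5%, simulation gives about 8-14% for a given active arm and 0.166, 0.197 and 0.257 for either arm. With no drift the either-arm figure is about 5%.

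**Step 5. Matched rates for rank-sum on change.** The exact two-sided size with 18 per arm is 0.0471, so a false rise in a given arm has probability 0.0471/2 = 0.024 whatever the shared drift. For either arm it is about 4% counting rises only, or about 8.5% two-sided.

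**Step 6. True 20% effect, shared decline of 10%.** The active arm's net change is +20 − 10 = +10%, so the values of p from step 4 apply.

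| ρ | Signed-rank shows a rise | Rank-sum on change | Planned rank-sum on week-24 count |
|---|---|---|---|
| 0.3 | 26% | about 48% | about 61% |
| 0.5 | 34% | about 61% | about 61% |
| 0.7 | 52% | about 82% | about 61% |

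With a shared decline of 20% the net change is zero and the signed-rank test shows a rise in about 3% of trials. Both between-arm tests are unaffected.

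**The case against.** The strongest reply is that the placebo-controlled question is already answered. Randomisation makes expected baselines equal, so the between-arm difference in mean week-24 count and in mean change have the same expectation. The planned rank-sum test on the week-24 count detects the assumed effect in about 61% of trials whatever the shared decline. This stands. A reader might infer that the trial lacks a controlled efficacy test, or that a test on change would have more power. The documents support neither. The first is contradicted by the planned Kruskal-Wallis test. The second depends on ρ, which is not given: at 0.3 the test on change does worse than the planned one.

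Second, no section adopts significant on drug, not significant on placebo, as a decision rule or says the within-arm p-values will be read as efficacy, and 14.2 speaks only of describing change. That also stands; the risk is of misreading, not of a stated wrong rule. Nor can one say that placebo data go unused, since the test may well be run in that arm too. What is missing is the comparison.

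Third, the Kruskal-Wallis test may have been intended for change. If so the gap closes, but its sentence names the six-month number, so the text has to be reconciled.

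Finally, a reader might infer that the entry rule (two counts below 10 million, 9.1.1) builds an upward drift into the signed-rank test by regression to the mean. That needs a screening sample to enter the baseline, and no section says so. A week-0 sample is scheduled (12.4.1); under an assumed log-normal model with that sample as baseline, the false-rise rate per arm is 2-3%, essentially the nominal 2.5%.

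**Conclusion.** The point holds in a limited form. As written, the only test of the change endpoint is uncontrolled, and change on drug is not tested against change on placebo. With no drug effect, the misleading pattern for a given active arm occurs in about 8-14% of trials with a shared 5% rise and 19-25% with 10%, against about 2.4% for a false rise by rank-sum on change. For either active arm the figures are about 16-26% and 34-38%, against about 4%. These sizes rest on the assumed drift, correlation, reading of 14.1's variance and normal changes; only the direction follows from the documents.

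The gain from correcting it is a valid controlled inference on change, not established extra power over the primary test. Severity is minor: a secondary endpoint in a pilot trial whose week-24 comparison stands.

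**What to change.** In section 14, replace the signed-rank sentence with wording such as:

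> *Change in total motile sperm count from baseline (the week-0 pre-dose sample) to week 24 will be compared between each active arm and placebo by a Wilcoxon rank-sum test on change, following a Kruskal-Wallis test on change. The between-arm difference and its 95% CI will be reported. These comparisons are supportive. Within-arm changes will be described only.*

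A rank ANCOVA of the week-24 count on baseline would serve equally well. A different baseline is also acceptable if fixed in advance.

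Separately, make the endpoint labels agree in the synopsis, section 14 and section 14.2. If the primary endpoint is the week-24 count between arms, remove the comparison with baseline and the word increase from its definition. If it is change, word the Kruskal-Wallis sentence for change.

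The cost is protocol wording; the samples are already scheduled. The downside is two supportive comparisons, with about an 8.5% chance of at least one false positive if unadjusted, or about 4% if they are read only after a significant Kruskal-Wallis test on change.
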